- Introduce new dose(s) arms if needed and enroll up to about 82 subjects per new arm
- Complete full enrolment for all efficacious arms (up to about 82 subjects per arm)
- Stop the study enrollment if all dose arms are stopped for safety or futility.

The total sample size (range from 328 to 408 subjects) varies depending on actual enrollment rate, number of dropped dose arm(s) and number of newly added dose arm(s). The details of interim analysis and the criteria to adapt dose arm(s) and stop for futility are specified in the [section 8.5](#).

Endpoints:

Co-Primary

- ACR20 response rate at Week 12
- ACR70 response rate at Week 12

Secondary

- Signs and Symptoms: ACR20/ACR50/70 over time
- Remission and change from baseline: DAS28-CRP, DAS-ESR, SDAI, CDAI, Boolean over time
- PK: Ctrough of BMS-986142
- Change in RAMRIS Scores of synovitis, osteitis, bone erosion and cartilage loss from baseline to Week 4 and Week 12

Statistical Analyses:

Efficacy analysis:

The co-primary endpoint ACR 20 and ACR70 response rate at Week 12 will be summarized for each treatment group using point estimate and 90% confidence intervals (CIs). Treatment difference of ACR 20/ACR70 response rate at Week 12 between each BMS-986142 arm versus placebo will be provided with point estimate and two-sided 95% CIs. The chi-square tests will be used to compare the ACR response rates at Week 12 between each of the active treatment arms and the placebo arm at type I error rate of 0.05. Within each treatment group, the statistical testing will be performed for ACR20 at level of 0.05 first. If it is statistically significant, then the statistical testing will be performed for ACR70. Otherwise, stop testing for this treatment group. All treatment groups will follow the

same testing procedure. All subjects who discontinue prematurely during the treatment period or receive rescue therapy will be counted as non-responder at subsequent visits.

Safety analysis:

All safety presentations will be based on the As-Treated population. Frequency distribution and individual listings of all adverse events, laboratory abnormalities and vital signs will be generated. Changes in clinical laboratory test results from baseline will be provided. No formal statistical tests on the treatment difference will be performed for any safety analyses.

Pharmacokinetic analysis:

Ctrough values will be descriptively summarized by treatment and study days.

[figure not shown]
[figure not shown]
[figure not shown]

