8.4.2 Efficacy Analyses

Primary efficacy analysis:

The Chi-square tests will be used to compare the ACR70 response rates at Week 12 between each of the active treatment arms and the placebo arm. The p-value will be provided for each comparison between the active treatment and the placebo arm. In addition, the difference of the response rates between each active treatment and the placebo will be estimated and their corresponding 95% confidence interval will be calculated.

All subjects discontinuing prematurely during the double-blind period, regardless of reason, will be counted as non-responders at subsequent visits. Summaries will be performed using mITT analysis population. The same analysis will be performed for ACR20 response at Week 12.

Secondary efficacy analysis:

- Proportion of subjects who achieve ACR20 over time from baseline to Week 12
- Proportion of subjects who achieve ACR50 over time from baseline to Week 12
- Proportion of subjects who achieve ACR70 over time from baseline to Week 12
- Proportion of subjects who achieve DAS28-CRP < 2.6 over time from baseline to Week 12
- Proportion of subjects who achieve DAS28-ESR < 2.6 over time from baseline to Week 12
- Proportion of subjects who achieve CDAI \leq 2.8 over time from baseline to Week 12
- Proportion of subjects who achieve SDAI \leq 3.3 over time from baseline to Week 12
- Proportion of subjects who achieve Boolean Remission over time from baseline to Week 12

For each of the above endpoints, the estimate and its corresponding 95% confidence interval will be calculated for the difference of the proportions between each active treatment arm and the placebo arm at the specified visit, similar to the primary analysis.

For each of the following endpoints, the mixed effect model will be fit with treatment and visit as the fixed effects and measurements within each subject as the repeated measurements. The baseline value will be added into the model as a covariate if necessary. Based on the mixed effect model, the estimate and 95% confidence interval will be calculated for the difference between each active treatment and the placebo at each specified visit:

- Change from baseline in DAS28-CRP score over time up to Week 12
- Change from baseline in DAS28-ESR score over time up to Week 12
- Change from baseline in CDAI score over time up to Week 12
- Change from baseline in SDAI score over time up to Week 12

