7 STATISTICAL ANALYSES

7.1 General Methods

The table below provides an overview of the efficacy analyses to be performed.

Table 1: Planned Efficacy Analyses

Measure of Interest (Primary and Secondary Efficacy Endpoints):	Analysis Method
Co-primary endpoints: ACR20 and 70 response rate at Day 85	Chi-Square test, two sided p-value will be provided. Point estimates and 95% CI of treatment difference.
Binary endpoints : ACR20, ACR50 and ACR70 response rate over time from baseline to Day 85; DAS28-CRP<2.6, DAS28-ESR<2.6, CDAI<=2.8, SDAI<=3.3 and Boolean remission over time from baseline to Day 85	Point estimate and 95% CI of response rate, point estimates and 95% CI of treatment difference.
Continuous endpoints: DAS28-CRP, DAS28-ESR, CDAI, SDAI, MRI scores (synovitis, osteitis, bone erosion and cartilage loss)	Mixed model analysis, point estimates and 95% CI for mean change from baseline within treatment groups, point estimates and 95% CI for mean change from baseline between treatment groups.

The Chi-square tests will be used to compare the ACR20 and ACR70 response rates at Day 85 between each of the active treatment arms and the placebo arm. The Chi-square p-value will be provided for each comparison between the active treatment and the placebo arm. Within each treatment group, the statistical testing will be performed for ACR20 at level of 0.05 first. If it is statistically significant, then the statistical testing will be performed for ACR70. Otherwise, testing will be stopped for this treatment group. All treatment groups will follow the same testing procedure. In addition, the difference of the response rates between each active treatment and the placebo will be estimated and their corresponding 95% confidence interval will be calculated. All subjects who discontinue prematurely during the treatment period or receive prohibited medications (refer to [Section 8.3](#)) will be counted as non-responder at subsequent visits.

For each of the binary endpoints, the estimate and its corresponding 95% confidence interval will be calculated for the difference of the proportions between each active treatment arm and the placebo arm at the specified visit, similar to the primary analysis except no p-values will be provided.

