7.3.2 Demography and Baseline Characteristics

Demographic and baseline disease characteristics will be summarized by randomized treatment group and overall based on the MITT analysis populations. For continuous variables, they will be summarized using means, standard deviations and ranges. The distribution of categorical variables such as gender, race etc. will be summarized by treatment group using frequency and percentage.

Demographic characteristics include the following:

- Age in years
- Weight in kgs
- Gender: Male, Female

- Race
- Ethnicity (Hispanic and Non-Hispanic)
- Region grouping scheme A (Latin America+East Europe and ROW) [details in [Appendix 2](#)]
- Region grouping scheme B (North America, Latin America, Europe and ROW) [details in [Appendix 2](#)]
- Stratification (MTX-IR vs. TNF-IR)

Baseline clinical characteristics include the following:

- Duration of disease in years
- Duration of disease (<=2 years, > 2 to 5 years, > 5 years to 10 years, > 10 years)
- ACR functional status classification
- RA classification (2010 ACR/EULAR criteria)
- Individual scores of each ACR components
- DAS28-CRP
- DAS28-ESR
- RF Status: Negative versus Positive
- ACPA Status: Negative versus Positive
- hsCRP (mg/L)
- ESR (mm/hr)
- MTX weekly dose
- Oral daily steroid dose (prednisone equivalents) in mg at Day 1
- Prior non-biologics DMARD therapy: Categorized number of non-biologic DMARDs use prior to randomization (0, 1, 2, >=3)
- Number of subjects with inadequate and/or intolerance to TNFi (overall Yes/No, then categorized by intolerant, no response, insufficient response, and loss of response. Note: subject can be included in more than one category)
- Number of subjects with a primary failure (i.e., insufficient response to the first course of Therapy) (Yes, No)
- Number of subjects with TNFi failures: 0, 1, 2, or >2

7.3.3 *Medical History and Prior Medication*

Medical history and prior medication information before the first study medication will be summarized by treatment group using relative frequencies. Listings of medical history and prior medication will be presented. The results will be based on the MITT analysis population.

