7.4.4 Anti-rheumatic Medication

For the purpose of this analysis plan, the term DMARDs will refer to non-biologic DMARDs. Anti-rheumatic medication summaries will be provided to present the medication use of corticosteroids, NSAIDs, and DMARDs. Number and percent of subjects receiving corticosteroids, NSAIDs, and DMARDs will be summarized by treatment group for MITT analysis population during the DB period.

In addition, the mean weekly MTX dose at scheduled visit and mean daily dose of corticosteroids during the DB period will be summarized.

A comprehensive listing of all concomitant medications will be also provided for the MITT analysis population.

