The conventions for dealing with missing data, procedures or intra-articular injections of joints (has impact on tender and swollen joint counts), restricted medications and high dose of corticosteroids are provided in [Section 8.2, 8.3, 8.5.1](#).

8.1.2 *Evaluation of DAS28-CRP and DAS28-ESR*

The DAS used in this protocol is the DAS using the 28-count subsets of tender/painful joints and swollen joints, together with either CRP or erythrocyte sedimentation rate ESR, to derive the, DAS28-CRP, and DAS28-ESR, which are calculated using the following formulae, respectively:

$$\text{DAS28-CRP} = 0.56 * \text{sqrt}(\text{TJC28}) + 0.28 * \text{sqrt}(\text{SJC28}) + 0.36 * \text{ln}(\text{CRP}+1) + 0.014 * \text{GH} + 0.96.$$

$$\text{DAS28-ESR} = 0.56 * \text{sqrt}(\text{TJC28}) + 0.28 * \text{sqrt}(\text{SJC28}) + 0.70 * \text{ln}(\text{ESR}) + 0.014 * \text{GH}.$$

where TJC28 is number of painful joints out of 28 joints, SJC28 is number of swollen joints out of 28 joints, GH is the general health or patients' global assessment of disease activity on a 100 mm VAS, ln is the natural logarithm, ESR is in mm/hour, and CRP is in mg/L.

8.1.3 *Evaluation of CDAI*

Calculation of Clinical Disease Activity Index (CDAI) is the simple linear sum of the outcome parameters: tender joint count (TJC) and swollen joint count (SJC) based on a 28-joint assessment, patient global assessment of disease activity (PGA: VAS 0–10 cm), and physician global assessment of disease activity (EGA: VAS 0–10 cm):

$$\text{CDAI} = \text{TJC28} + \text{SJC28} + \text{PGA} + \text{EGA}.$$

CDAI Remission responder is defined as a CDAI score less than or equal to 2.8.

8.1.4 *Evaluation of SDAI and Boolean-based Remission*

Calculation of Simple Disease Activity Index (SDAI) is the simple linear sum of the outcome parameters: tender joint count (TJC) and swollen joint count (SJC) based on a 28-joint assessment, patient global assessment of disease activity (PGA: VAS 0–10 cm), physician global assessment of disease activity (EGA: VAS 0–10 cm) and C-reactive protein (CRP in mg/dL) as shown below:

$$\text{SDAI} = \text{TJC28} + \text{SJC28} + \text{PGA} + \text{EGA} + \text{CRP}.$$

SDAI Remission responder is defined as a SDAI score less than or equal 3.3.

Remission by Boolean-based definition: Subject must satisfy all of the followings:

$$\text{TJC28} \leq 1; \text{SJC28} \leq 1; \text{PGA} \leq 1; \text{CRP} \leq 1 \text{ mg/dL}$$

8.1.5 *Evaluation of HAQ Disability Index*

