8.3 Determination of Responder Data

Subjects who receive 1 or more IA or IM injection during the double-blind period of study will be classified as ACR non-responder on and after the time of the first IA or IM injection and up to the end of the double-blind period. Subjects who receive a high oral steroids course that is defined as the use of either any oral dose (equivalent of prednisone) higher than baseline (Day 1) use for ≥ 1 day or any oral dose (equivalent of prednisone) $>10\text{mg/day}$ for ≥ 1 day will be counted as non-responder at all visits subsequent to the date of dose that is higher than the baseline dose.

Subjects who increase MTX use (versus baseline) during the double-blind period will be counted as non-responder at all visits subsequent to the earliest date of increased MTX dose.

Subjects who receive any DMARDs (other than MTX) during the double-blind period will be counted as non-responder at all visits subsequent to the earliest date of DMARDs.

These rules will apply to binary endpoints including ACR20/50/70, DAS28-CRP <2.6, DAS28-ESR <2.6 and remission status defined by CDAI, SDAI and Boolean definition.

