8.5 Missing Measurements

8.5.1 *Imputation of Missing Data for Binary Variables*

This imputation is applicable for all binary variables (ACR20/50/70, DAS28-CRP <2.6, DAS28-ESR <2.6, and remission status defined by CDAI, SDAI and Boolean definition).

If the response cannot be assessed due to missing data or a subject's early discontinuation, the following conventions will be implemented in a sequence:

- Any subject who prematurely discontinues the trial during the double-blind period after receiving study medication will have data imputed as non-responder at all scheduled protocol visits subsequent to the point of discontinuation up to the end of the double-blind period.
- After any imputation above or none, if for some reason the binary variable still can't be determined, including the case where baseline data is missing, then its value will be set to non-responder.

For listings, missing responses will be presented as missing.

8.5.2 *Imputation of Missing Data for Continuous Variables*

For the analysis of changes from baseline values (e.g., individual components of ACR, DAS28-CRP, and DAS28-ESR etc), missing values will be dealt with via the longitudinal repeated measures analysis assuming MAR (missingness at random).

For all safety (including laboratory measurements), and PK measures, missing values will not be imputed.

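### The SAP 8.3 list that decides responder status does not, read literally, reach a biologic started on study, and is not tied to the synopsis term rescue therapy

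*SAP*

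**What the plan says.** SAP 8.3 is the operative rule for both co-primary endpoints and for remission by DAS28-CRP, DAS28-ESR, CDAI, SDAI and the Boolean definition. It has four triggers: an intra-articular or intramuscular injection (no drug named), a high oral steroid course, an increase in MTX over baseline, and a DMARD trigger: "Subjects who receive any DMARDs (other than MTX) during the double-blind period will be counted as non-responder". No biologic is named.

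SAP 7.4.4, which introduces the anti-rheumatic medication summaries, says "For the purpose of this analysis plan, the term DMARDs will refer to non-biologic DMARDs".

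Three other places describe the same kind of rule in different terms:

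- SAP 7.1 assigns non-response to "All subjects who discontinue prematurely during the treatment period or receive prohibited medications" and refers to Section 8.3 for the detail. SAP 8.1.1 likewise sends the reader to 8.2, 8.3 and 8.5.1, where the conventions for "restricted medications and high dose of corticosteroids are provided in".
- The protocol synopsis, under Statistical Analyses, says "All subjects who discontinue prematurely during the treatment period or receive rescue therapy will be counted as non-responder at subsequent visits". Rescue therapy is not defined in the visible text.
- Protocol 8.4.2 covers discontinuation only: "All subjects discontinuing prematurely during the double-blind period, regardless of reason, will be counted as non-responders at subsequent visits".

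SAP 8.5.1 adds a backstop: "Any subject who prematurely discontinues the trial during the double-blind period after receiving study medication will have data imputed as non-responder".

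**The concern.** A programmer who applies the 7.4.4 definition to 8.3, as its wording invites, would leave a subject as a responder after an added biologic, provided the subject remains in the trial and has an evaluable Week 12 visit. A response reached on another active drug would then be credited to the randomized arm. On placebo this narrows the treatment difference; on an active arm it widens it. The documents do not say where such subjects would be more common.

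SAP 7.1 and the synopsis both suggest that additional anti-rheumatic treatment was meant to count as non-response, but neither gives a drug list that would settle the matter. If the choice were first made after unblinding, it would be a post hoc decision on the co-primary endpoints.

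**Working it through.** **Is it a contradiction or a gap?** SAP 7.1 names a category (prohibited medications) and sends the reader to 8.3 for its content. It supplies no rival list, so 8.3 is the definition and the defect is one of coverage. The synopsis uses another category, rescue therapy, with no pointer to 8.3. Protocol 8.4.2 uses neither category.

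**How far does the 7.4.4 definition reach?** Its words are plan-wide. Against that, it opens a section on medication summaries, and SAP 7.3.2 still writes "Prior non-biologics DMARD therapy: Categorized number of non-biologic DMARDs use prior to randomization", where the qualifier would be redundant if the definition held throughout. Both readings are open.

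**Who is left uncovered?** A subject who leaves the trial is a non-responder under SAP 8.5.1. Protocol 5.3 says the early termination visit should precede any prohibited concomitant drug. However, protocol 3.6.1 keeps subjects who ask to stop study drug in the study and under follow-up, and SAP 7.4.2 defines stopping study therapy separately. A subject who stops drug, starts a biologic and has a visit in the Day 72 to 99 window (SAP 8.7) is not clearly caught by 8.5.1. SAP 7.1 and protocol 8.4.2 would catch that subject if premature discontinuation includes stopping drug; neither says so.

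**Size.** The documents give no count of biologic starters, so this part is illustrative. The formula is two-proportion power with pooled variance under the null, continuity-corrected, two-sided 0.05, n = 82:

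power = Φ[(p₁ − p₀ − 1/n − 1.96·SE₀)/SE₁], with SE₀ = √(2p̄(1−p̄)/n) and SE₁ = √([p₀(1−p₀) + p₁(1−p₁)]/n).

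The plan's own figures first:

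- Protocol 8.1, ACR70, 2.5% vs 19.5%: (0.170 − 0.0122 − 1.96 × 0.0489)/0.0470 = 1.32, power 91% (stated about 90%).
- SAP 5, ACR70, 2.5% vs 16.5%: SE₀ = 0.0458, SE₁ = 0.0445, power 80% (stated about 80%).
- ACR20: 33% vs 67% gives 99% (protocol states above 99%); 22% vs 53% gives 98% (SAP states 98%).

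Response rate assumed for an added approved drug, from the documents' historical figures: ACR70 2.5% + 17%/2 = 11% (protocol) or 2.5% + 7% = 9.5% (SAP); ACR20 67% (protocol) or 53% (SAP). Retained placebo responders k = starters × rate, and p₀ becomes base + k/82.

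| Placebo starters per 82 (assumed) | ACR70 k, protocol / SAP | ACR70 power, protocol / SAP | ACR20 power, protocol / SAP |
|---|---|---|---|
| 0 | 0 / 0 | 91% / 80% | 99% / 98% |
| 2 | 0.22 / 0.19 | 89% / 78% | 98% / 97% |
| 4 | 0.44 / 0.38 | 88% / 76% | 97% / 95% |

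If both arms gained the same k as with 4 starters, ACR70 power would be 89% (protocol inputs) or 79% (SAP inputs).

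One whole retained ACR70 responder on placebo would need 1/0.11 = 9.1 to 1/0.095 = 10.5 starters, that is 11% to 13% of 82.

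**The case against.** The strongest reply is that the visible text nearly closes the route. Prohibited drugs are expected only after the early termination visit, and protocol 8.4.2 makes discontinuers non-responders regardless of reason. The text on restricted treatments and part of the discontinuation criteria is redacted, and SAP Appendix 1 is not shown. Any of these may name biologics or require discontinuation, and text removed by redaction cannot be held against the plan. If 7.4.4 governs only its own section, the 8.3 trigger already covers biologics. Most of this stands: it makes the case rare. It does not settle the wording of 8.3, because the definition is expressed plan-wide and the early termination timing is an expectation.

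The illustration also leans towards a larger effect. It gives starters the full approved-drug response although the drug would begin partway through 12 weeks, it puts starters on placebo only, and it keeps 82 per arm although the synopsis says enrolment stopped before the planned number.

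A reader might infer three stronger points that the documents do not support:

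- That 8.3 contradicts SAP 7.1. It does not, since 7.1 defers to 8.3.
- That ACR70 power would drop to 84% (protocol inputs) or 69% (SAP inputs). Those are the figures for one retained placebo responder, which needs about 9 to 11 starters on placebo; nothing in the documents suggests that many.
- That stable intramuscular background MTX is meant to be non-response. Protocol 3.3.1 admits parenteral MTX, protocol 3.3.2 pairs intramuscular and intra-articular with glucocorticosteroids, SAP 8.2 lists steroid injection among joint procedures, and 8.3 has its own MTX rule based on an increase. Steroid is the likely meaning, so only the wording needs attention.

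**Conclusion.** Wrong as written, but minor. The operative list in SAP 8.3, combined with the 7.4.4 definition, literally omits biologics and is not linked to the synopsis rule on rescue therapy or to protocol 8.4.2. The effect is confined to subjects who start a biologic and are not classed as discontinuers. It may be nil. With 2 to 4 such placebo subjects per 82, ACR70 power falls by about 1 to 3 points on the protocol inputs and 2 to 4 points on the SAP inputs, and ACR20 power stays at 95% or above. These figures rest on an assumed number of starters, on the documents' historical response rates and on full planned enrolment. The direction of any bias in the final comparison is unknown. Redacted text could remove the gap altogether.

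**What to change.** Before database lock and unblinding:

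1. State in SAP 8.3 that, for responder status, the DMARD trigger covers biologic as well as non-biologic DMARDs other than MTX.
2. Limit the SAP 7.4.4 definition to the medication summaries in that section.
3. Make prohibited medications (SAP 7.1), rescue therapy (protocol synopsis) and protocol 8.4.2 all refer to the single list in SAP 8.3.
4. As a secondary wording point, state which drug class the injection clause in 8.3 covers. Reconcile it with protocol 3.1 and SAP 2.1 (intramuscular injections not permitted, no drug named), protocol 3.3.1 (parenteral MTX admitted) and protocol 3.3.2, so that stable parenteral background MTX is not coded as non-response by accident.

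These changes concern responder coding only. The cost is a phrase in 8.3, a limiting phrase in 7.4.4, cross-references to one list, and a clarification of the injection clause. No new data are needed, because SAP 7.4.4 already plans a listing of all concomitant medications.
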